3.0 INTRODUCTION

3.1 The Urea/NO Cycle

A critical biochemical pathway to maintain metabolic homeostasis is the urea/nitric oxide (NO) cycle [1]. The urea/NO cycle is involved in the intermediary metabolism of the key amino acids citrulline and arginine, forming a critical bridge between urea/NO cycle activities in the liver and the nitric oxide synthase (NOS) system present in other tissues for cell signaling and immune functioning. Alterations in the urea cycle in the liver can lead to systemic effects, including oxidant stress and inflammation (Figure 1). Kupffer cells, the largest fixed macrophage population in the body, have the capacity to react to various inflammatory insults, including infectious agents, and release inflammatory cytokines like TNF α , IL-1, and IL-8, into the circulation [2,3]. In addition, although the full urea cycle is limited to the liver, other organs, including the lung, contain many of the cytosolic enzymes, including nitric oxide synthase (NOS). The degree to which Kupffer cells and other macrophages, including pulmonary macrophages, deal with oxidant stress, and maintain metabolic homeostasis is closely related to NOS function and availability of arginine. NOS, in its natural coupled form, utilizes arginine as a substrate for producing nitric oxide (NO) and citrulline. However, when uncoupled, NOS preferentially produces the superoxide radical (O_2^-). This free radical reacts with NO to form peroxynitrite and other ROS, which stimulate monocytes to produce and release additional proinflammatory cytokines [4,5], further propagating and prolonging the inflammatory cascade (Figure 1).

[figure not shown]

[figure not shown]
Figure 1

The rate-limiting enzyme catalyzing the first committed step of ureagenesis in the urea/NO cycle, carbamoyl-phosphate synthetase 1 (CPS1) (Figure 2), is highly tissue specific, with function and production limited to the liver and small intestine. CPS 1 forms carbamoyl phosphate from ammonia,

carbon dioxide, and ATP-derived phosphate, which is then joined to ornithine by ornithine transcarbamylase (OTC) to form citrulline. Citrulline is not found in any enzyme or structural protein, thus its principal function is its role in the urea cycle. The vast majority of both CPS1 and OTC are found in hepatic mitochondria. The remaining enzymes, arginine-succinate synthase (AS), arginine-succinate lyase (AL), and arginase are cytoplasmic enzymes with wide tissue distribution, including the lung [6]. Sequential actions of AS and AL convert citrulline to arginine, the only non-dietary source of arginine. The liver either takes up citrulline from GI production/absorption or manufactures it from ornithine and converts it to arginine, releasing the latter into the bloodstream. Ordinarily in the liver, urea is cleaved from arginine to regenerate ornithine. However, arginine exported from the liver also serves as a substrate for systemic NOS, heme proteins that catalyze oxidation of L-arginine to NO and L-citrulline. NOS is found in all cells in at least one of three isoforms: nNOS (neuronal, constitutive), eNOS (endothelial, constitutive), and iNOS (inducible). NOS substrate, arginine, is manufactured in the cell from citrulline or is supplied to the body by the liver or the kidney. Under normal physiological conditions, homeostasis of NOS activity is maintained by levels of both citrulline and arginine.

Within the endothelial cell, the chemically bound caveolar HSP-90 pathway restricts NO production to arginine derived from HSP-90-bound citrulline. In addition, we have recently observed that in human vascular endothelial cells, extracellular citrulline and not arginine, is the effective precursor of NO production. These findings suggest that circulating levels of citrulline may be more predictive of NOS function than arginine levels. Citrulline serves as a negative feedback inhibitor on NOS and arginine, couples NOS to produce NO preferentially over O_2^- .

There are clear links between a poorly functioning urea/NO cycle in the liver, altered balance of citrulline and arginine, decreased NO production in the lung and increased oxidant stress, which results in increased pulmonary vascular resistance, development of ALI and mortality. We also reason that restoration of citrulline/arginine balance through citrulline administration will safely re-establish homeostasis of NOS, lower oxidative stress, and reduce inflammation without resulting in overproduction of NO and precipitating hypotension.

3.2 The Urea/NO Cycle and Oxidative Stress in Acute Hypoxic Respiratory Failure

Although the biochemical relationships and interlocking metabolic pathways in health and disease are complex, the urea cycle and NO metabolites play an integral role in the inflammatory cascade and oxidative stress reactions of many disease states. Homeostasis of redox signaling is contingent on many aspects which are complex, take place in a variety of tissues and depend on a balance of competing factors, including the amount and location of arginine, citrulline, NO and superoxide generation as well as whether or not these reactions are coupled [7]. As such, citrulline and arginine form a critical bridge between urea/NO cycle activities in the liver and the NOS system for cell signaling and immune functioning in the liver, lung, microvasculature, and elsewhere in the body. Intracellular pools of citrulline primarily and arginine determine NO synthesis and play a major role in oxidative stress. It has been shown *in vitro* that iNOS superoxide generation is decreased substantially with physiologic concentrations of arginine and is abolished completely in similarly designed nNOS systems [8,9].

Inducible NOS is upregulated during physiologic stress; however, if NOS substrate is insufficient then NOS can uncouple and switch from NO generation to production of damaging peroxynitrites. We hypothesized that NOS substrate levels are low in patients with COVID 19 (SARS-CoV2) and that low levels of the NOS substrate citrulline would be associated with end organ damage including acute respiratory syndrome. We further hypothesized that arginine levels would not be associated with acute respiratory syndrome because of substrate channeling from citrulline to NO. Furthermore, citrulline enters the cell with relatively little competition through neutral amino transport, while arginine uses dibasic amino acid transport, and we detect very little free arginine inside cells, findings that also favor a primary role for citrulline availability in regulation of NOS coupling.

In inflammatory conditions, ROS are produced within endothelial cells and neutrophils. These free radicals interact with endothelial cell membranes, especially in the lung, via lipid peroxidation, causing altered membrane fluidity and function. In acute respiratory failure and other inflammatory states, the urea cycle/NO system plays an integral role in this process. Intracellular deficiency of arginine and its precursor citrulline is common due to a combination of poor intake of substrate and reduced activity of CPS1, due to oxidation then proteolytic degradation. In addition, AS and AL are often co-induced along with inducible NOS (iNOS), especially in macrophages, making the citrulline-arginine cycle hyperactive in many inflamed tissues, including the lung in patients with severe infections. The resultant decreased production and increased consumption of citrulline and arginine results in dramatically decreased intracellular and plasma levels of both [10], which have been linked to abnormal liver function, lung injury, coma, and death [11-13]. The hepatic and systemic deficiency of arginine, like those seen in severely septic or BMT patients, contributes to the uncoupling of NOS. Uncoupled NOS preferentially generates O_2^- rather than NO [8,13-15] (Figure 2). Additionally, citrulline becomes a conditionally essential amino acid in these inflammatory states as levels fall below those needed to maintain negative feedback inhibition on NOS, resulting in hyperactive NOS and overproduction of both NO and O_2^- . Increased NO production results in vasomotor instability and contributes to the hypotension seen in septic shock. The subsequent reaction between NO and superoxide generates peroxynitrite [16], which contributes to vasomotor dysfunction [17,18] and may inactivate catecholamines [19]. Peroxynitrite also reacts with unsaturated fatty acids resulting in lipid peroxidation [20]. Lipid peroxidation of the endothelial cell membranes result in altered membrane structure and function which leads to capillary permeability and the syndrome of ALI. In addition, the resultant oxidative stress stimulates monocytes to release more pro-inflammatory cytokines, further potentiating the inflammatory cascade and subsequent end-organ damage, especially lung injury.

3.3 Citrulline Replacement

As mentioned, citrulline's main function appears to be related to the urea/NO cycle, and it may be a better molecule than arginine to support this function for several reasons. First, citrulline has free access to the mitochondrial matrix and facile entry into the urea cycle pathway. Specific dibasic amino acid transporters allow shuttling of ornithine and citrulline across the mitochondrial membrane [21]. Dietary manipulation of citrulline content clearly influences urea cycle intermediate levels. Addition of citrulline to the diet of arginine deficient rats supports a normal level of arginine in the blood, reduces plasma ammonia to normal, and eliminates excretion of orotic acid in the urine [22]. Recycling of citrulline to arginine is well documented in several species and in many tissues [23]. In a study of 30 patients with Reye's syndrome, a disease whose characteristics are similar to sepsis with depression of CPS1 activity and markedly decreased plasma citrulline levels, provision of enteral citrulline (n=8) promoted more rapid lowering of plasma ammonia and among the sickest patients, showed a trend toward reduced mortality compared to untreated patients (n=14) (50% vs. 88%; P=0.075) (DeLong 1982). In healthy adults, patients undergoing chemotherapy for bone marrow transplant, and children undergoing congenital heart surgery, supplementation with citrulline (either oral or IV) supports a higher plasma level of arginine and is associated with decreased *in vivo* lipid peroxidation suggesting that citrulline is superior to arginine as a method of enhancing circulating arginine and reducing oxidative stress.

In elegant studies of plasma arginine, citrulline, ornithine, and NO flux using stable isotopic tracers [24-30], Castillo and colleagues showed that: (1) Arginine-free intake does not significantly affect the rate of either *in vivo* arginine or citrulline biosynthesis, despite a decline in the plasma arginine flux and free arginine concentration. (2) Temporary arginine-free diet did not reduce total nitrate output (i.e. NO production was not reduced). Together, these suggest that a reduction in arginine does not limit citrulline

or NO production (3) Labeled citrulline leaves the plasma and is metabolized by a full turn of the urea cycle before reentering as arginine, (4) Oral administration of ^{15}N -arginine results in a nearly five-fold greater recovery of tracer in $^{15}\text{NO}_3$ than when an equimolar amount of tracer is given intravenously, documenting significant splanchnic production of NO. Administration of IV citrulline significantly bypasses the splanchnic circulation, thus limiting the splanchnic production of NO. (5) About 15% of the plasma arginine turnover is associated with urea formation; only 1.2% is associated with NO production. As arginase is upregulated in sepsis, the amount of arginine available as substrate for NOS is further reduced. Although this may decrease NO production somewhat (likely limited due to the low percentage of arginine converted to NO normally), it also alters homeostasis by uncoupling NOS and limiting the amount of NO available to scavenge free radicals. Citrulline is resistant to arginase and our data demonstrate that citrulline administration produces a more consistent plasma level of arginine than arginine administration itself.

3.4 COVID-19 (SARS-CoV2) and Acute Hypoxemic Respiratory Failure Requiring Invasive Mechanical Ventilation

Although reports in the US literature on COVID-19 (SARS-CoV2) and critical illness is limited, a recent case series published in the New England Journal of Medicine detailed the clinical course of 24 critically ill adults with acute hypoxemic respiratory failure and confirmed COVID-19 infection (SARS-CoV2) in Seattle, Washington at 3 hospitals in the University of Washington health care system (106). The mean age was 64 +/- 18 years with a range of 23-97 years and 63% were male. Patients had symptoms an average of 7 days before hospital admission. Of the 24 patients, 18 or 75% required invasive mechanical ventilation but after exclusion of 3 patients who had "do not intubate" directives the percentage was to 18/21 or 86% requiring invasive mechanical ventilation. The median duration of invasive mechanical ventilation was 10 days (IQR 7-12) and overall mortality was 50% in this critically ill population.

3.4 Summary

The body lives in a delicate balance of homeostasis. The urea/NO cycle plays a critical role in maintaining redox homeostasis and as such, also plays a role in regulating inflammation. The biochemical relationships are complex and depend on inter-organ transfer, membrane transport, and intracellular compartmentation. However, data above demonstrate that citrulline, arginine, and NO are critical in maintaining this homeostasis through their regulation of NOS. Inflammation, especially from infection, results in decreased activity of CPS1 and increased activity of arginase, which decreases levels of both citrulline and arginine. These decreased levels result in dysregulated and uncoupled NOS, which drives both overexuberant NO production and formation of ROS. Both the NO production and ROS further exacerbate the inflammatory cascade, resulting in other organ dysfunctions, including acute lung injury. Both inflammation and oxidative stress have been shown to be driving forces for the development of ALI and *regulated* NOS function is vital to reducing both. Both plasma citrulline and arginine are deficient in sepsis and levels are inversely associated with development of ALI. Furthermore, citrulline replacement safely increases plasma levels of both citrulline and arginine in healthy volunteers, BMT patients, adults with sepsis, children with sickle cell disease, and children after congenital heart surgery. It seems highly likely that citrulline therapy in the setting of COVID-19 (SARS-CoV2) induced acute hypoxemic respiratory illness will safely increase citrulline and arginine levels and help re-establish NOS homeostasis, resulting in NO production in compartments that are more homeostatically appropriate so as to reduce pulmonary vascular resistance and enhance coupling of NOS to minimize superoxide production thus reducing free radical mediated ALI.

4.0 OBJECTIVES

4.1 Primary Endpoints (objectives)

The primary objectives of the study are as follows:

- The primary biochemical objective of this trial is to evaluate the effects of intravenous L-Citrulline on plasma levels of citrulline and arginine in patients admitted to the hospital with COVID-19 infection (SARS-CoV2) and acute hypoxic respiratory symptoms requiring oxygen therapy. An association of plasma amino acid levels to clinical outcomes may serve as surrogate marker for response.
- The primary safety objective is a beneficial effect of intravenous L-Citrulline on hemodynamics.
- The primary clinical objective is to evaluate the difference in the length of time to an intubation event in hours from the start of study infusion between the study arms.

4.2 Secondary Endpoints (objectives)

The secondary objectives of this study are as follows:

- To evaluate the safety of intravenous L-Citrulline compared to placebo as measured by incidence of reported adverse events.
- To evaluate the effect of intravenous L-Citrulline compared to placebo as measured by the total length of all mechanical ventilation, including non-invasive modalities such as high flow nasal cannula and BiPAP and oxygen therapy.
- To evaluate the effect of intravenous L-Citrulline compared to placebo on Hospital all-cause mortality
- To evaluate the effect of intravenous L-Citrulline compared to placebo on lengths of ICU and hospital stay
- To evaluate overall difference in intubation rates
- To evaluate overall duration of mechanical ventilation from consent and post-infusion

5.0 STUDY DESIGN

5.1 Study Description

This is a randomized, double-blind, placebo-controlled, phase II study to evaluate the safety and efficacy of intravenous L-Citrulline in reducing the length of time from the start of study infusion to an intubation event in hospitalized acutely ill patients with an acute hypoxic respiratory illness due to COVID-19 infection (SARS-CoV2). Patient's age of 18 years old and less than 65 years old inclusive with COVID-19 infection (SARS-CoV2) will be included in the study.

Only subjects hospitalized at UAMS and requiring oxygen for an acute hypoxic respiratory illness due to COVID-19 (SARS-CoV2) will be included in this study. Study drug administration will occur exclusively in the hospital.

In addition, subjects will receive standard supportive care for acute hypoxic respiratory illness and failure.

Up to 66 participants ages 18 years to 65 years, inclusive, who meet all the inclusion criteria and none of the exclusion criteria will be randomized into the study over approximately 6-9 months.

The study consists of an initial Study Drug bolus followed by a continuous infusion for a maximum of 10 days. The safety and efficacy will be evaluated through hemodynamic monitoring, laboratory assessment, oxygenation status, and biomarker measurements through study day 10. Adverse events will be monitored through study day 10. Clinical outcomes, including all-cause mortality, ICU length of stay, and hospital length of stay will be assessed through hospital discharge with a telephone follow up at D28 and D60, if discharged earlier.

5.1.1 Randomization, Stratification, and Blinding

Participants will be randomly assigned to one of two study groups. Randomization assignments will be determined prior to initiation of the study using a random size permuted block design. Randomization will be stratified by age group with participants divided into 2 age groups of 18-49 years and 50-65 years. After obtaining informed consent, the signed informed consent document will be faxed to the investigational pharmacy. Upon receipt, the investigational pharmacy will begin preparation of the study material infusion. Assignment will be communicated electronically using Medrio randomization system. Once the study drug material is prepared, it will be sent to the bedside for administration via the bedside nurse under the oversight of one of the site investigators and/or study coordinator. After baseline hemodynamic assessments, participants will be randomized to either placebo or citrulline in a 1:1 fashion stratified by age group. The participants, nurses, physicians, study coordinators and investigators will remain blinded to whether participants are receiving placebo or L-citrulline throughout the study. The investigational pharmacy will be unblinded and will be responsible for maintaining the blinding of investigators, participants, nurses, and primary medical team. The investigational pharmacy will deliver the correct infusion(s) to the patient's bedside every 24 hours. The placebo and study drug solutions will be identical appearing on delivery to the ICU where the drug will be administered.

5.1.2 Study Assessments

The assessment of efficacy will include collection of plasma for analysis of citrulline and arginine levels at day 1 hours 0, 2, 12, and the alternating morning of study days the infusion is running for a maximum of 10 days, i.e., on days 2, 4, 6, 8 and 10. A patient will exit the study early if they have been weaned off all oxygen support before 10 days. Additional efficacy measures will include clinical outcomes, including progression of acute lung injury and lengths of hospital and ICU stay.

The assessment of safety will include collection of hemodynamic measurements at least every 4 hours on a hospital unit and--if a patient is critically ill in an ICU--hourly while the study material is infusing and for 12 hours after completion of the infusion in each patient. Hemodynamic measurements will be converted to a vasopressor dependency index for analysis if a patient becomes critically ill. Adverse event reporting will also serve as a means of safety analysis. Additional safety measures will be biochemical and hematologic laboratory measurements. The biochemical laboratory measurements, including liver function tests (ALT, AST, bilirubin, alkaline phosphatase), kidney function tests, and electrolytes, along with hematologic laboratory measurements, including complete blood count and platelet count, will be collected when available for any study day in order to evaluate for adverse events.

5.2 Treatment Arms and Study Drug Administration

All study material infusions (including the initial boluses) will be administered intravenously through a dedicated peripheral line or a dedicated port of a central line using a volumetric or syringe pump. The infusion will be restarted as soon as possible after any stoppages and will continue through day 10 unless the patient exits the study early. Regardless of amount of time the infusion is stopped, time missed during any stoppage will not be added to the end of the infusion.

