APPENDIX A: Schedule of Events

Measurement	Day 0 (baseline)	Day 1	Day 2	Day 3	Day 4	Day 5	Day 6	Day 7	Day 8	Day 9	Day 10	Day 11	Day 12-DC	Day 28 ^e Follow-up	Day 60 ^e Follow-up
Informed Consent	X														
Demographics- Hx & Px	X														
Eligibility Assessment	X														
Pregnancy Test	Xc														
Study Drug Administration		X	X	X	X	X	X	X	X	X					
Vital Signs		X	X	X	X	X	X	X	X	X	X	X	X		
Mean Arterial Pressure		Xa,b,d	X	X	X	X	X	X	X	X	X	X			
Vasopressor Dosages		Xa,b,d	X	X	X	X	X	X	X	X	X	X			
Basic Metabolic Panel		A	A	A	A	A	A	A	A	A	A	A			
CBC		A	A	A	A	A	A	A	A	A	A	A			
LFTs		Ab	A	A	A	A	A	A	A	A	A	A			
D-dimer blood draw		Xa,b	X		X		X		X		X		X		
CRP		Xa,b	X		X		X		X		X		X		
5 ml blood for citrulline etc.		Xa,b	X		X		X		X		X				
SaO2/ FiO2 ratio		X	X	X	X	X	X	X	X	X	X	X			
PaO2		X	X	X	X	X	X	X	X	X	X	X			
ABG		A	A	A	A	A	A	A	A	A	A	A			
Hospital status		X	X	X	X	X	X	X	X	X	X	X	X	X	X
ICU status		X	X	X	X	X	X	X	X	X	X	X	X	X	X
Non-invasive ventilation status		X	X	X	X	X	X	X	X	X	X	X			
Invasive ventilation status		X	X	X	X	X	X	X	X	X	X	X			
ConMed Review		X	X	X	X	X	X	X	X	X	X	X	X	X	X

Adverse Event Review		X	X	X	X	X	X	X	X	X	X	X	X	X	X	X
----------------------	--	---	---	---	---	---	---	---	---	---	---	---	---	---	---	---

a= measurement should be recorded or performed at hours 0, 2 and 12

b= Day 1 hour 0 samples/procedure must be collected/recorded before study drug is administered.

c= only perform if patient is of childbearing potential

d= must be collected 15 minutes prior to administration of study medication

e= Day 28 and Day 60 are telephone follow ups

X= Study Procedure A= Standard of Care

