## **STUDY ASSESSMENTS**

The assessment of efficacy will include collection of plasma for analysis of citrulline and arginine levels at 2 hours, 12 hours, and the alternating morning of study days the infusion is running for a maximum of

10 days, i.e., on days 2, 4, 6, 8 and 10. A patient will exit the study early if they have been weaned off all oxygen support before 10 days. Additional efficacy measures will include clinical outcomes, including progression of acute lung injury and lengths of hospital and ICU stay.

The assessment of safety will include collection of hemodynamic measurements at least every 4 hours on a hospital unit and--if a patient is critically ill in an ICU--hourly while the study material is infusing and for 12 hours after completion of the infusion in each patient. Hemodynamic measurements will be converted to a vasopressor dependency index for analysis if a patient becomes critically ill. Adverse event reporting will also serve as a means of safety analysis. Additional safety measures will be biochemical and hematologic laboratory measurements. The biochemical laboratory measurements, including liver function tests (ALT, AST, bilirubin, alkaline phosphatase), kidney function tests, D-dimer tests, CRP and electrolytes, along with hematologic laboratory measurements, including complete blood count and platelet count, will be collected when available for any study day in order to evaluate for adverse events.

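### Appendix A ends study drug at Day 9 while the body text infuses through day 10: a contradiction of up to 24 h that would put the Day 10 amino acid sample across the stop

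*Protocol*

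**What the plan says.** The protocol's body text is consistent that day 10 is an infusion day:

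- Section 5.2: the infusion "will continue through day 10 unless the patient exits the study early".
- Section 5.2.3: after an interruption, the infusion may not run past the close of study day 10.
- Sections 2.0, 5.1 and 7.2.2: the course lasts at most 10 days.
- Section 5.1.2: plasma is taken on "the alternating morning of study days the infusion is running for a maximum of 10 days", and day 10 is in the list that follows. The SAP, under Study Assessments, uses the same wording.
- Section 7.2.2: the drug is discontinued on Day 10, with no hour given. The same section counts all times from the start of study drug at Hour 0.

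Appendix A differs. Its "Study Drug Administration" row is marked on Days 1 to 9 and is blank on Day 10. Its "5 ml blood for citrulline etc" row is marked on Days 1, 2, 4, 6, 8 and 10. No footnote explains the blank cell. Appendix C gives the Day 10 sample a window of 2 h either side but does not mention the infusion.

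**The concern.** Section 7.2 names Appendix A as the summary of when every study procedure is done, so the table is what bedside and pharmacy staff are likely to work from. The supplied text has no rule on whether table or text prevails. A team that follows the drug row would stop at the end of Day 9, and a team that follows section 5.2 would stop at the end of Day 10.

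Two things are then at stake. Patients who need the full course could lose up to a day of drug. The Day 10 citrulline, arginine and NOx values could also mix samples on infusion with samples just off it, under one visit label. Both documents test a treatment-by-time effect in a mixed model, so a lower level after the stop could be read as an effect that wanes during treatment.

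**Working it through.** **1. Is the blank cell real?** The Appendix A header has 15 visit columns: Day 0, Days 1 to 11, Day 12-DC, Day 28 and Day 60 (1 + 11 + 3 = 15). The drug row has 15 cells: one empty (Day 0), nine marked (Days 1 to 9) and five empty (Day 10, Day 11, Day 12-DC, Day 28, Day 60), and 1 + 9 + 5 = 15. The row lines up with the header. Sliding it one column to the right would leave Day 1 undosed, although footnote b places Hour 0 on Day 1. A column shift is therefore not the explanation.

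**2. Does the table agree with itself?** Section 7.2.2 ends the drug on Day 10 and lists the drug and the citrulline draw together as what no longer continues. In Appendix A the draw reaches Day 10 and the drug does not.

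**3. Length of the infusion.** With Hour 0 at the start of Day 1 (section 7.2.2 and footnote b):

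- body text: 10 × 24 = 240 h
- Appendix A: 9 × 24 = 216 h
- difference: 240 − 216 = 24 h, and 24 / 240 = 10.0%

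Adding the Day 10 mark gives ten marked days, or 240 h, which reproduces the 10-day maximum. The gap is at most 24 h because section 7.2.2 gives no hour for the Day 10 stop.

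**4. Dose, at the capped rate.** The inputs from section 5.2.1 are a bolus of at most 1500 mg and an infusion of at most 700 mg/h. The hourly cap applies from 700 / 9 = 77.8 kg.

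- table: 1.5 + 216 × 0.7 = 152.7 g
- text: 1.5 + 240 × 0.7 = 169.5 g
- difference: 16.8 g, and 16.8 / 169.5 = 9.9%

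**5. Position of the Day 10 sample.** Appendix C ties Day 2 to 24 h from Hour 0. Carrying that anchor forward is an assumption, because Appendix C states it for Day 2 only. It puts Day 10 at 9 × 24 = 216 h, with a window of 214 to 218 h.

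| Stop | Sample relative to stop |
|---|---|
| Appendix A, 216 h | from 2 h before to 2 h after |
| Body text, 240 h | 22 to 26 h before (240 − 218, 240 − 214) |

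Under the body text the sample is clearly on infusion. Under the table it straddles the stop. The documents give no half-life for citrulline, so the fall in level after the stop is not estimated.

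**6. Reach.** Day 10 is one of seven post-dose times in the protocol (2 h, 12 h, days 2, 4, 6, 8 and 10). It is one of six in the SAP endpoint lists, which omit day 6.

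**The case against.** The strongest reply is that the body text already settles the matter. Sections 5.2, 5.2.3 and 7.2.2 agree on day 10, Appendix A is only a summary, and one blank cell looks like an omitted mark. Nothing shows that any site would follow the table against explicit dosing text. This stands as to intent and is why the point is minor. It does not make the table right: staff are sent there for the schedule, and the entry they find is wrong.

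A mark lost when the PDF was read cannot be strictly excluded, since the adverse event row of the same table carries one surplus mark. The drug row itself fills its columns exactly, so nothing in that row suggests a loss.

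The marks might be read as pharmacy supplies, since the infusion is delivered to the "bedside every 24 hours". Nine supplies still end at 9 × 24 = 216 h.

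Three stronger readings are tempting and are not supported:

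- *Study time is undefined, so days may be calendar days.* A reader could then place the stop at midnight and the 8 AM sample well after it, with a larger proportional loss. Section 7.2.2 counts all times from Hour 0. Its 8 AM target is a loose aim for draws and blood pressure records. No section states a midnight stop.
- *The "Mean Arterial Pressure" row, marked to Day 11, confirms a Day 10 stop*, because section 5.1.2 wants hemodynamics "for 12 hours after completion of the infusion in each patient". Most daily rows run to Day 11, so those marks are compatible with a Day 10 stop but do not point to it.
- *The biochemical results are compromised.* On the Hour 0 clock the sample falls at most 2 h after the table's stop, and without a half-life no loss of level can be claimed.

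**Conclusion.** The contradiction holds and is minor. The Appendix A drug row gives 216 h where the body text gives up to 240 h, a gap of up to 24 h, or 10% of a full course (16.8 g at the capped rate). If the table is followed, the Day 10 sample straddles the stop instead of falling 22 to 26 h before it.

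The 24 h rests on the Hour 0 clock of section 7.2.2 and on a stop at the end of the last marked day. The sample position also rests on carrying the Day 2 anchor of Appendix C forward to Day 10.

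Only patients still on infusion at day 10 are concerned, and only one sampling time for endpoints that the SAP classes as secondary. The primary analysis of time to intubation, the sample size and the day 4 biochemical variable are untouched.

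**What to change.** - Appendix A: mark Day 10 in the study drug row.
- Section 7.2.2: state that study drug stops at the end of study day 10, to match section 5.2.3.
- Section 7.2.2: require that the Day 10 sample be drawn before the infusion is stopped, and that the actual stop time and sample time be recorded.

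The cost is one mark and one or two sentences in the protocol. There is no extra visit or sample, and the SAP needs no change.
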